**Table 2. Time Point Response: Patients with Nontarget Disease Only**

Nontarget Lesions	New Lesions	Overall Response
CR	No	CR
Non-CR/non-PD	No	Non-CR/non-PD a
Not all evaluated	No	NE
Unequivocal PD	Yes or No	PD
Any	Yes	PD

Abbreviations: CR = complete response; NE = inevaluable; PD = progressive disease; SD = stable disease.

a non-CR/non-PD is preferred over SD for nontarget disease.

### Frequency of Tumor Re-Evaluation

A baseline tumor evaluation must be performed within 4 weeks before patient begins study treatment. Frequency of tumor re-evaluation while on and adapted to treatment should be protocol-specific and adapted to the type and schedule of treatment. In the context of Phase 2 studies where the beneficial effect therapy is not known, follow-up every 6-8 weeks is reasonable. Normally, all target and non-target sites are evaluated at each assessment using the same method. However, bone scans may need to be repeated only when CR is identified in target disease or when progression in bone is suspected.

### Confirmatory Measurement/Duration of Response

#### *Confirmation:*

The main goal of confirmation of objective response in clinical trials is to avoid overestimating the response rate observed. The confirmation of response is particularly important in *nonrandomized trials* where response (CR/PR) is the primary end point. In this setting, to be assigned a status of PR/CR, changes in tumor measurements must be confirmed by repeat assessments that should be performed no less than 4 weeks after the criteria for response are first met. To confirm a response of CR, a full assessment of all target and nontarget lesions that were present at baseline must occur, including those measured by bone scan. To confirm a PR or SD, a full assessment of target lesions that were present at baseline must occur; assessment of nontarget lesions is not required.

However, in *randomized trial* (Phase 2 or 3) or studies where SD or progression is the primary endpoints, confirmation of response is not required. But, elimination of the requirement may increase the importance of central review to protect against bias, in particular of studies which are not blinded.

In the case of SD, follow-up measurements must have met the SD criteria at least once after start of treatment at a minimum interval not less than 6 weeks measured from first dose.

#### *Duration of Overall Response*

The duration of overall response is measured from the time measurement criteria are first met for CR or PR (whichever is first recorded) until the first date that disease is recurrent or objective

progression is observed (taking as reference for progressive disease the smallest measurements recorded on study).

The duration of overall CR is measured from the time measurement criteria are first met for CR until the first date that recurrent disease is objectively documented.

*Duration of Stable Disease*

Stable disease is measured from the start of the treatment (in randomized trials, from date of randomization) until the criteria for objective progression are met, taking as reference the smallest sum on study (if the baseline sum is the smallest, that is the reference for calculation of progressive disease).

**Independent Review of Response and Progression**

When objective response (CR + PR) is the primary end point, and when key drug development decisions are based on the observation of a minimum number of responders, it is recommended that all claimed responses be reviewed by an expert(s) independent of the study. If the study is a randomized trial, ideally reviewers should be blinded to treatment assignment.

---

**Attachment 10. Protocol JSCB Guidelines for the Management of Immune-Related Adverse Events**

---

### Guidelines for the Management of Potential Toxicities Encountered with Immuno-Oncology Agents

System Organ Class	Adverse Event	CTCAE, Version 4.0 Grade (if applicable) and/or Symptoms a		Treatment Plan b
		Grade	Symptoms	
Endocrine	Thyroid issues		Asymptomatic, with TSH $<0.5 \times$ LLN or $>2 \times$ ULN	Continue drug and include free T4 in subsequent cycles.
			Symptomatic	Continue drug. Administer thyroid replacement.
	Hypotension, altered mental status, headache, fatigue		Endocrine issues aside from thyroid (for example, hypophysitis, diabetes mellitus)	Withhold drug. Administer steroids (1-2 mg/kg/d prednisone).  Resume drug when symptoms resolve and are stable on hormone replacement. In case of adrenal crisis, administer stress-dose steroids.  Permanently discontinue for Grade 3 or 4.
Gastrointestinal	Diarrhea, abdominal pain, blood in stool	2		Withhold drug for 1 wk. Administer antidiarrheal medication and check etiology.  Resume drug when symptoms resolve to Grade <1. If >5 days' duration despite antidiarrheals, begin steroids (0.5 mg/kg/d prednisone); can resume drug during taper when symptoms resolve to Grade <1.
	Diarrhea, ileus, perforation	$\geq 3$		Withhold drug and administer 1-2 mg/kg/day prednisone (no steroids if possible perforation); discontinue drug if Grade 3 persists or Grade 4. If $>3$ days despite steroids, add nonsteroid immunosuppressive.
	Symptomatic pancreatitis	1 or 2		Withhold drug. Administer steroids (1-2 mg/kg/d prednisone). Can resume drug during taper.
		$\geq 3$		Permanently discontinue drug. Administer steroids (1-2 mg/kg/d prednisone). Can resume drug during taper.

System Organ Class	Adverse Event	CTCAE, Version 4.0 Grade (if applicable) and/or Symptoms a		Treatment Plan b
		Grade	Symptoms	
Hepatobiliary	Liver abnormality		AST or ALT $>5 \times$ ULN but $\leq 20 \times$ ULN  AND  total bilirubin $\leq$ ULN	Discuss with sponsor and consider continuing protocol treatment provided patient remains without other evidence of liver toxicity.
			AST or ALT $>20 \times$ ULN  AND  total bilirubin $\leq$ ULN	Discuss with sponsor and consider holding protocol treatment until AST/ALT becomes $\leq 20 \times$ ULN.
			AST or ALT $>5 \times$ ULN  AND  total bilirubin $>$ ULN	Withhold drug. Administer steroids (1-2 mg/kg/d prednisone). Consider resuming protocol treatment once total bilirubin $\leq$ ULN.  Discontinue protocol therapy permanently if bilirubin does not return to below the ULN within 3 wk of holding drug.
		3 or 4	GGT or alkaline phosphatase	Continue protocol treatment provided patient remains without other evidence of liver toxicity.
Musculoskeletal	Muscle abnormality		CK $>2.5 \times$ but $\leq 10$ ULN  AND  Serum and urine myoglobin $\leq$ ULN	Discuss with sponsor and consider continuing protocol treatment provided patient remains without other evidence of muscle or renal toxicity.
			CK $\geq 2.5 \times$ ULN  AND  Serum and urine myoglobin $>$ ULN	Withhold drug. Administer steroids (1-2 mg/kg/d prednisone). Consider resuming protocol treatment once serum and urine myoglobin $\leq$ ULN.  Discontinue protocol therapy permanently if serum and urine myoglobin does not return to below the ULN within 3 wk of holding drug.

System Organ Class	Adverse Event	CTCAE, Version 4.0 Grade (if applicable) and/or Symptoms a		Treatment Plan b
		Grade	Symptoms	
Nervous	Weakness, paresthesia (for example, Guillain-Barré syndrome, myasthenia gravis)		No impact on activities of daily living (ADL)	Withhold drug. Resume drug when symptoms resolve.
			Impact on ADL	Withhold drug. Administer appropriate medical intervention and steroids (1-2 mg/kg/d prednisone). Can resume drug during taper and after discussion with sponsor.
Respiratory	Dyspnea, hypoxia, pneumonitis	1		Consider to withhold drug. Resume drug when stable.
		2	Mild to moderate symptoms	Withhold drug. Administer steroids (1-2 mg/kg/d prednisone). Can resume drug during taper.
		≥3	Severe	Permanently discontinue drug. Administer steroids (1-2 mg/kg/d prednisone).  If >2 days despite steroids, add nonsteroid immunosuppressive.
Renal and urinary	Elevated creatinine, decreased urine output, blood in urine, edema	1	<1.5 × baseline	Continue drug.
		2 to 3	>1.5 × ULN but <6 × ULN	Withhold drug. Administer steroids (1- 2 mg/kg/d prednisone). If symptoms resolve to Grade ≤1, taper steroids over 1 month. Can resume drug during taper.
			OR  >1.5 × baseline	If elevations persist >7 days or worsen treat with Grade 4 recommendations.
		4	>6 × ULN	Permanently discontinue drug. Administer steroids (1-2 mg/kg/d prednisone).
Skin	Rash, pruritus		≤50% skin affected	Withhold drug. Start supportive medications for pruritus, for example, hydroxyzine/loratadine. If symptoms persist or worsen after 1 wk, administer topical or systemic steroids. Resume drug if rash improves to mild (localized) and steroid dose <7.5 mg.
			Stevens-Johnson syndrome, toxic epidermal necrolysis, necrosis, bullous or hemorrhagic lesions	Permanently discontinue drug. Begin steroids (1-2 mg/kg/d prednisone).

Abbreviations: ADL = activities of daily living; ALT = alanine aminotransferase; AST = aspartate aminotransferase; CTCAE = Common Terminology Criteria for Adverse Events; I.V. = intravenous(ly); LLN = lower limit of normal; TSH = thyroid-stimulating hormone; ULN = upper limit of normal.

a If definition of grade not specified, use CTCAE, Version 4.0 definition.

b Treatment plan should always include a thorough workup of the issue to rule out other potential etiologies.

Note: Other steroid options can be given at equivalent doses. For severe cases, recommend using IV steroids. For adrenal crisis, mineralocorticoid also needs to be added to stress-dose IV steroids. Also, steroids should be tapered over 1 month once symptoms improve to  $\leq$  grade 1, and drug should not be restarted until taper over at least 1 month complete. During steroid use, add prophylactic antibiotics for opportunistic infections. Immunosuppressive refers to infliximab or cyclophosphamide.

---

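### Attachment 10 tells the investigator both to stop LY3022855 permanently and that it may be resumed during the taper in Grade 3 or higher symptomatic pancreatitis

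*Protocol*

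**What the plan says.** Attachment 10 lists a treatment plan by organ system and grade. For symptomatic pancreatitis of Grade 3 or higher the plan is "Permanently discontinue drug. Administer steroids (1-2 mg/kg/d prednisone). Can resume drug during taper". For Grade 1 or 2, in the row above, it is "Withhold drug. Administer steroids (1-2 mg/kg/d prednisone). Can resume drug during taper".

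A Note under the table sets a general rule: steroids are tapered over 1 month once symptoms reach Grade 1 or lower, and "drug should not be restarted until taper over at least 1 month complete".

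Three other parts of the protocol bear on this:

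- Section 7.2.1.2.1 sends investigators to Attachment 10, calls it a guideline, and lets local standards override it.
- Section 7.2.1 makes continued dosing after a toxicity subject to sponsor agreement. For the toxicities in Table JSCB.3, which include Grade 3 or 4 nonhematologic events, it allows a hold of at most 4 weeks and then a reduced dose from the next cycle, if the investigator thinks it appropriate and the sponsor agrees.
- Section 6.3.1 requires discontinuation for unacceptable toxicity, without defining that term or naming pancreatitis.

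**The concern.** A drug that has been stopped for good cannot be resumed while steroids are being tapered. An investigator who consults the table for a severe pancreatitis finds an order to stop beside a permission to re-dose. The sponsor physician asked to agree would consult the same cell. What is at stake is patient safety and consistent handling of a severe toxicity, not an estimate or an error rate.

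The second matter is of the same kind but weaker. Several rows let the drug restart during the taper, the Note says to wait until the taper is finished, and no sentence ranks one above the other.

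**Working it through.** The plan gives no figure to reproduce, so the check sets the wording side by side.

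**Step 1. Cells that order a permanent stop outright.**

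| Attachment 10 cell | Stop instruction | Restart sentence |
|---|---|---|
| Symptomatic pancreatitis, Grade 3 or higher | "Permanently discontinue drug. Administer steroids (1-2 mg/kg/d prednisone). Can resume drug during taper" | Yes, in the same cell |
| Respiratory, Grade 3 or higher | "Permanently discontinue drug. Administer steroids (1-2 mg/kg/d prednisone" | None |
| Renal, Grade 4 | Same words as respiratory | None |
| Severe skin reactions | "Permanently discontinue drug. Begin steroids (1-2 mg/kg/d prednisone" | None |

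Of 4 such cells, 1 has a restart sentence and 3 do not.

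**Step 2. Does the table elsewhere combine stopping and restarting coherently?** It does, but with a stated condition each time. The non-thyroid endocrine cell allows resumption and reserves the permanent stop for Grade 3 or 4. The cells for transaminases with raised bilirubin and for CK with raised myoglobin make the permanent stop depend on failure to recover within 3 weeks. The severe pancreatitis cell states no condition.

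**Step 3. Is it a PDF artefact?** No. The Grade 1 or 2 row keeps its own complete text, and the amendment summary in Attachment 11 prints the severe pancreatitis cell in the same words.

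**Step 4. Does another section settle it?** No. Under Section 7.2.1 and Table JSCB.3, a Grade 3 or 4 nonhematologic toxicity can be held and re-dosed at a lower level, so the general rule does not supply the stop. Section 6.3.1 leaves unacceptable toxicity to judgment. The guideline status in Section 7.2.1.2.1 does not say which of the two recommendations is the recommendation.

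**Step 5. Rows against the Note.** Leaving the severe pancreatitis cell aside, five rows expressly allow restart during the taper:

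1. Grade 2 diarrhea, if steroids are used: "can resume drug during taper when symptoms resolve to Grade <1".
2. Grade 1 or 2 symptomatic pancreatitis: "Withhold drug. Administer steroids (1-2 mg/kg/d prednisone). Can resume drug during taper".
3. Nervous system, with impact on daily living: "Can resume drug during taper and after discussion with sponsor".
4. Respiratory, Grade 2: same words as item 2.
5. Renal, Grade 2 to 3: "If symptoms resolve to Grade ≤1, taper steroids over 1 month. Can resume drug during taper".

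The rash row is arguable. It allows restart once the rash is mild and the steroid dose is below 7.5 mg. If systemic steroids are being tapered, that implies restart on a low dose, although a finished taper would also satisfy it. Neither the table footnotes, the Note nor Section 7.2.1.2.1 ranks rows against Note.

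**Step 6. The Note against the maximum hold.** Under the Note, time off drug is at least the days needed to reach Grade 1 or lower plus 1 month of taper. Section 7.2.1 allows 4 × 7 = 28 days. Taking a month as 28 to 31 days (an assumption), the two fit only if improvement is immediate and the month is counted as 4 weeks. The cap applies to Table JSCB.3 toxicities, subject to the exceptions listed there. Among the five rows it can therefore reach the Grade 3 part of the renal row and any nervous-system event of Grade 3 or 4, but not the rows limited to Grade 2 or lower. It can also reach Grade 3 or higher diarrhea, which has no restart rule of its own and so falls to the Note.

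**The case against.** The strongest reply is that this is a one-sentence slip in a table that local practice may override. The cell opens with the order to stop, so re-dosing by oversight is unlikely. The sponsor must agree before dosing continues. The readable text reports no pancreatitis with this drug, and Section 7.2.1.2 does not list it among the events to monitor closely. All of this stands as a limit on harm. None of it says which instruction is meant.

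On the second matter, the rows can be read as specific exceptions to a general Note. The renal row, which names the 1-month taper and still allows restart within it, points that way. This is a fair inference, but the protocol does not state it.

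Two stronger readings are tempting and should be resisted:

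- A reader might infer that nearly every steroid row with a restart rule contradicts the Note. The non-thyroid endocrine, transaminase-with-bilirubin and CK-with-myoglobin rows set a condition for resuming and are silent on the taper. Each can be applied together with the Note, as a minimum condition plus a completed taper, so they are not conflicts.
- A reader might infer a drug-specific danger from the CK-with-myoglobin dose-limiting toxicity reported in Section 5.4.5. That case occurred in Study JSCA at 150 mg weekly, a dose not used in this trial, and the matching row does not mention restart during the taper.

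**Conclusion.** The severe pancreatitis cell is wrong as written: an internal inconsistency in an operative instruction, affecting 1 of the 4 cells that order a permanent stop outright. I rate it between minor and should-fix. That the restart sentence is the error, rather than the stop order, is inferred from the row above and the three parallel cells; the sponsor's clinicians should confirm it. No sample size, error rate or analysis changes, and the documents give no number of patients affected.

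The mismatch between rows and Note is a secondary observation: five express cases, with rash arguable. Which should govern is a clinical decision that the documents do not settle, so it is put to the sponsor as a question, with no preferred answer.

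**What to change.** Delete the closing sentence that permits resumption during the taper from the Grade 3 or higher symptomatic pancreatitis cell, after confirmation by the sponsor's clinical team. The cost is one sentence in one cell.

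Separately, ask the sponsor to state under the table whether a row's restart rule or the Note governs when they differ, and to check the choice against the 4-week maximum hold for Table JSCB.3 toxicities. If the rows govern, one sentence in the Note is enough to settle precedence, though the fit of Grade 3 or higher diarrhea with the hold limit still needs checking. If the Note governs, the five rows, and the rash row where systemic steroids are given, need rewording, and Section 7.2.1 may need a sentence on holds prolonged by a taper. Neither choice touches the design, sample size or analysis.

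### Attachment 10 gives two answers on re-dosing after steroids for an immune-related event, and its severe-pancreatitis cell both stops LY3022855 for good and lets it resume

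*Protocol*

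**What the plan says.** Protocol Section 7.2.1.2.1 sends investigators to Attachment 10 when symptoms suggest an immune-related event. The attachment is a table of events with a Treatment Plan for each, followed by a Note.

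The Note asks for a one-month steroid taper once symptoms reach Grade 1 or better, and adds "drug should not be restarted until taper over at least 1 month complete". It is not tied to any organ class or grade.

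Five rows say otherwise:
- Diarrhea Grade 2, if steroids are needed: "can resume drug during taper when symptoms resolve to Grade <1".
- Pancreatitis Grade 1 or 2, and respiratory Grade 2, in the same words: "Withhold drug. Administer steroids (1-2 mg/kg/d prednisone). Can resume drug during taper".
- Nervous events that affect daily activities: "Can resume drug during taper and after discussion with sponsor".
- Renal Grade 2 to 3: "taper steroids over 1 month. Can resume drug during taper".

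The pancreatitis row for Grade 3 or higher reads "Permanently discontinue drug. Administer steroids (1-2 mg/kg/d prednisone). Can resume drug during taper". The skin row for up to half the skin affected reads "Resume drug if rash improves to mild (localized) and steroid dose <7.5 mg".

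Two other passages bear on the point. Section 7.2.1 requires the sponsor's agreement before a patient continues after a toxicity. Section 7.2.1.2.1 calls Attachment 10 a guideline that local standards may supersede. The SAP has no rule on re-dosing.

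**The concern.** The question is a safety one: may a patient with immune toxicity receive LY3022855 again while still on steroids for it, or must the taper finish first? Five rows say yes and the Note says no. Nothing in the Protocol ranks one above the other, so a site that follows a row and a site that follows the Note both comply.

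The severe-pancreatitis cell is worse because it fails without the Note. One sentence ends treatment permanently and another allows it to resume. On the second reading, a patient with the more severe form of the event is re-exposed although the same cell says treatment is over.

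**Working it through.** The plan states no figure to reproduce. The check is a count of the table, then arithmetic on what the conflict means for one patient.

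**1. Rows that give or allow steroids: 14.** They are non-thyroid endocrine; diarrhea Grade 2; diarrhea Grade 3 or higher; pancreatitis Grade 1 or 2; pancreatitis Grade 3 or higher; AST/ALT with raised bilirubin; CK with raised myoglobin; nervous with effect on daily activities; respiratory Grade 2; respiratory Grade 3 or higher; renal Grade 2 to 3; renal Grade 4; skin up to 50%; severe skin.

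**2. Rows that stop drug permanently: 4.** Pancreatitis Grade 3 or higher, respiratory Grade 3 or higher, renal Grade 4 and severe skin. Only the pancreatitis cell also carries a resume sentence. Its last two sentences repeat the Grade 1 or 2 cell above it, which suggests a carry-over error.

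**3. The other 14 − 4 = 10 rows set against the Note:**

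| Row's restart rule | Rows | Compatible with the Note? |
|---|---|---|
| Resume during taper | 5: diarrhea 2, pancreatitis 1–2, nervous, respiratory 2, renal 2–3 | No |
| Resume below 7.5 mg steroid | 1: skin up to 50% | No, if systemic steroids are used |
| A condition that can be met together with the Note | 3: endocrine, AST/ALT with bilirubin, CK with myoglobin | Yes |
| None given ("discontinue drug if Grade 3 persists or Grade 4" is only a stopping rule) | 1: diarrhea 3 or higher | Yes; only the Note governs |

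5 + 1 + 3 + 1 = 10. The renal row shows that row and Note do not describe different tapers: it prescribes the Note's own one-month taper and then allows drug during it.

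**4. Doses that the five rows allow and the Note forbids.** Schedules are from Table JSCB.1, for events below Grade 3 at full dose. Scheduled doses falling in a 30-day taper, over all possible start days:
- Dosage C, every 7 days: 4 to 5, which is 4 × 100 to 5 × 100 = 400 to 500 mg.
- Dosage D, every 14 days: 2 to 3, which is 200 to 300 mg.
- Dosage A, every 14 days: 2 to 3.
- Dosage B, days 0 and 7 of every 21: 2 to 4. For example, days 0, 7, 21 and 28 give 4; a window opening on day 8 holds only days 21 and 28.

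With a 28-day month the counts are 4 at C, 2 at D and A, and 2 to 3 at B. These are ceilings, because the rows do not say when in the taper drug resumes. A restart at day 15 leaves 15 days, hence 2 to 3 doses at C and 1 to 2 at D.

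**5. Skin row.** The row gives no starting dose or taper shape. Assume a 75-kg person (the weight used for illustration in Section 5.4.5), prednisone at 0.5, 1 or 2 mg/kg/day (S = 37.5, 75 or 150 mg) and a linear 30-day taper. The dose falls below 7.5 mg after 30 × (1 − 7.5/S) days: 24, 27 or 28.5. That is 6, 3 or 1.5 days before the Note would allow restart. If only topical steroid is used, the conflict may not arise.

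**The case against.** The strongest reply is that a specific row ordinarily governs and a general Note fills the gaps. The renal row, which sets a one-month taper and allows drug during it, looks deliberate. This is a fair reading, but the Protocol does not state it and it cannot rescue the severe-pancreatitis cell. What stands is that nothing shows the Note to be the intended rule. A reader might infer that the Note must win because it is more cautious; that would be a clinical preference, not something the documents settle.

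Second, the practical harm is limited. This is one centre and about 40 enrolled patients, with sponsor agreement required each time and a guideline that local standards may supersede. In the text I have of Section 5.4.5, the toxicities described are mainly CK and AST elevations, including a Grade 3 CK event with myoglobin. The AST/ALT and CK steroid rows are compatible with the Note. All of this stands and lowers the expected impact. None of it tells the site or the sponsor which instruction to follow, since both consult the same page.

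Third, a reader might infer a clash with the 4-week maximum hold in Section 7.2.1, because a month's taper started after recovery runs past it, so that recovered patients would be forced off drug. The documents do not support this. That section ties the hold to recovery and discontinues a patient only if toxicity has not returned to baseline or below Grade 2 within 4 weeks of the last dose. A recovered patient who is still tapering does not meet that trigger.

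**Conclusion.** Wrong as written. The pancreatitis cell for Grade 3 or higher is self-contradictory, and five further rows permit what the Note forbids. The skin row is a minor additional conflict, a matter of days under the assumed tapers and only with systemic steroids. The per-patient ceiling is 4 to 5 doses at Dosage C, 2 to 3 at A and D, and 2 to 4 at B, assuming a 30-day taper and re-dosing from its first day. How often steroids will be needed cannot be known from the documents.

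A reader might go further and infer damage to the primary immunomodulatory data or to the evaluable set. The documents give no basis for that, and it is not claimed. This is an inexpensive safety correction that should be made, not a flaw in the trial's design or analysis.

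**What to change.** (a) In the pancreatitis row for Grade 3 or higher, delete the sentence that allows drug to resume during the taper.

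(b) State one restart rule. The sponsor chooses between:
- **Keep the Note.** Delete the resume-during-taper wording from the five rows, and align the skin row where systemic steroids are used. It would help to define a complete taper as off the steroid given for the event or back to the pre-event dose, because Section 7.5 lets prostate cancer patients take prednisone up to 10 mg/day. The cost is about a month's longer hold for a patient who is benefiting.
- **Let the row prevail.** Say so, and limit the Note's restart clause to rows that give no rule of their own. On the present table that is only diarrhea Grade 3 or higher. The five rows would then have no stated steroid ceiling for re-dosing, which the sponsor should weigh.

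Section 7.2.1 needs no change on this account. Excluding the taper from the 4-week limit would remove the only stated cap on hold time. Either option is a few words in Attachment 10, with no new data, visits or patients.
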